9.1.1 GENERAL

Descriptive statistical methods will be used to summarize the data from this study with hypothesis testing performed for primary and secondary endpoints. These include number of subjects (n), mean, median, standard deviation, minimum, and maximum for continuous data, and frequencies and percentages for categorical data. All data collected during the study will be reported and analyzed.

Unless specified otherwise, all statistical testing will be two-sided and performed using a significance (alpha) level of 0.05.

All statistical analyses will be conducted using PASW 19.

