9.3 SAMPLE SIZE CALCULATIONS

A two-sided logrank test with an overall sample size of 225 subjects (113 in the control group and 112 in the treatment group) achieves 86.1% power at a 0.05 significance level to detect a hazard ratio of 1.74 when the proportion of wounds healed in the control group is 0.5. The study lasts for 12 weeks with all subjects beginning the study together (no accrual periods). The proportion dropping out of the control group is 0.033 per week. The proportion dropping out of the treatment group is 0.0083 per week. The proportion switching from the control group to another group with a hazard ratio equal to that of the treatment group is 0.

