9.4 RANDOMIZATION

Randomization will be stratified by age of wound at the first screening visit (1-6 months and > 6 months).

The randomization algorithm will employ blocks of 2 and 4, with random selection of block sizes (Pass 11).

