9.7 STATISTICAL METHODS

MISSING DATA

Missing data may be the result of missed visits, subjects lost to follow-up or who have died, or data not available (e.g., smoking status).

Missing primary endpoint data within 12 weeks from start of study will not be imputed for ITT populations as these will constitute right-censored data in the time to heal analysis. The last visit for which data are available will constitute the start of censoring (healing outcome). For secondary endpoints within 12 weeks from start of study, the last observation carried forward (LOCF) principle will be used for ITT populations.

For adjusted analyses of primary and secondary endpoints, missing data for covariates used to adjust analyses may be imputed in separate models when the missing data for each covariate is $\leq 30\%$ and it can be reasonably demonstrated that the missing data for each covariate are MCAR.

FINAL ANALYSIS

Analysis can be started when database lock for the trial is initiated. In regard to statistical modeling, the initial list of independent variables will be examined for correlation between pairs. In the event that

correlation (however calculated) exceeds 0.7, a selection will be made between the 2 variables to avoid possible issues of co linearity and variance inflation.

The following analysis will be conducted:

1. Flow chart (subjects)
2. Overall trial statistics (enrollment dates, site numbers, numbers of subjects)
3. Demographics between groups at baseline (no statistical testing but identification of likely trial imbalances)
4. Count of subjects in each group
5. Primary endpoints within 6 and 12 weeks (time to heal; previously defined by groups) will be analyzed by Kaplan-Meier and log rank test (unadjusted); and then Cox regression to adjust for the following variables (with and without covariate imputation):

- Site
- Year enrolled (if trial lasts 2 years or more)
- Treatment group
- Initial area at randomization (cm²)
- Initial wound depth (cm)
- Age of wound at enrollment (days)
- Smoking status
- Prior VLU
- Pain score at randomization
- Patient age
- Gender
- Ethnicity/race
- VCS score
- Diabetes
- Patient on pain medications
- Smoking status
- BMI
- Infection episodes

6. Secondary endpoints will be analyzed as follows:

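### The primary log-rank test is not stratified by wound age, the factor used to stratify randomisation. It is valid, but stratifying is a free, probably small, gain in efficiency.

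*Combined protocol and SAP*

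**What the plan says.** Section 9.4 reads: "Randomization will be stratified by age of wound at the first screening visit (1-6 months and > 6 months"). No other stratification factor is named.

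Section 9.7 (Final Analysis, item 5) says that the primary endpoints at 6 and 12 weeks "will be analyzed by Kaplan-Meier and log rank test (unadjusted"). Cox regression follows, with a long covariate list that includes wound age in days. H1 in section 9.2 also names the log-rank test, without strata, and makes the Cox step depend on a significant log-rank result. Item 5 lists the Cox step without that condition.

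Section 9.3 sizes the trial on a two-sided log-rank test with an "overall sample size of 225 subjects (113 in the control group and 112 in the treatment group"), which "achieves 86.1% power at a 0.05 significance level to detect a hazard ratio of 1.74". Control healing is taken there as 50%. No strata enter that calculation.

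**The concern.** Stratified randomisation balances the arms within each wound-age level. If older wounds heal more slowly, a pooled log-rank test compares two mixtures of fast and slow healers. Its variance estimate takes no account of the within-stratum balance, and the pooled hazard ratio is pulled towards 1 as the faster healers leave the risk set. Both effects make the test conservative.

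At stake is some power in the test that decides the primary hypothesis. Choosing wound age as the only stratifier suggests that the sponsor expects it to matter, but the primary test does not use it. The later Cox model does not make up for this. Under H1 it runs only once the log-rank has succeeded, and under either wording the log-rank is the test named for the hypothesis.

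**Working it through.** **1. Inputs.** From section 9.3: 113 control and 112 treated subjects, hazard ratio (HR) 1.74, 50% control healing at 12 weeks, no accrual period, and weekly drop-out of 0.033 (control) and 0.0083 (treatment). From section 9.1.1: two-sided alpha of 0.05. From section 9.4: two wound-age strata, with blocks of 2 and 4. The documents do not give the share of ulcers older than 6 months or the healing HR of younger versus older wounds. These are assumed at 30%, 50% and 70%, and at 1, 1.5, 2 and 3.

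**2. Reproducing the 86.1%.** Assume exponential healing and drop-out.
- Healing hazards per week: control −ln(0.5)/12 = 0.0578; treatment 1.74 × 0.0578 = 0.1005.
- Drop-out hazards: −ln(1 − 0.033) = 0.0336; −ln(1 − 0.0083) = 0.0083.
- Expected events per arm: n × λ/(λ + δ) × [1 − exp(−12(λ + δ))], where λ is the healing hazard and δ the drop-out hazard. This gives 47.6 + 75.4 = 123.0.
- Schoenfeld: √(123/4) × ln 1.74 − 1.96 = 1.11, power 86.7%.
- Freedman: √123 × 0.74/2.74 − 1.96 = 1.04, power 85.0%.
- Lakatos-type calculation: 85.7%.

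The stated figure reproduces for a log-rank test without strata.

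**3. Unstratified and stratified tests on the same simulated data.** There were 4,000 trials per scenario, with weekly visits and permuted blocks within stratum. With p the share of older ulcers and HRw the wound-age HR, the younger-stratum control hazard λ solves (1 − p)exp(−12λ) + p exp(−12λ/HRw) = 0.5. The older-stratum hazard is λ/HRw, and the treatment HR is 1.74 within each stratum. The unstratified statistic is (O − E)/√V; the stratified one is Σ(O − E)/√ΣV, summed over the two strata.

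12-week power, unstratified → stratified (%):

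| Wound-age HR | 30% older | 50% older | 70% older | Gain (points) |
|---|---|---|---|---|
| 1.0 | 85.9 → 85.7 | 85.1 → 85.1 | 86.0 → 85.6 | −0.4 to 0 |
| 1.5 | 85.0 → 85.7 | 84.7 → 85.4 | 84.6 → 85.6 | 0.7 to 0.9 |
| 2.0 | 83.5 → 85.6 | 83.1 → 85.4 | 83.1 → 85.2 | 2.1 to 2.3 |
| 3.0 | 80.6 → 84.8 | 77.1 → 83.9 | 78.0 → 84.6 | 4.2 to 6.8 |

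Gains were taken before rounding; their simulation standard errors are 0.1 to 0.4 points.

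**4. Variations, all with 50% older ulcers, at wound-age HR 1, 1.5, 2 and 3.**
- 6-week comparison, same hazards, drop-out of 0.0083 per week assumed in both arms: 69.3 → 69.3, 69.7 → 70.1, 68.8 → 70.1 and 65.3 → 69.9%. The gains before rounding are 0, 0.4, 1.3 and 4.5 points.
- 12-week comparison with treated healing held at 1 − 0.5^1.74 = 70%: gains of 0, 0.7, 1.9 and 4.0 points.

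**5. Validity under the null (50% older ulcers).** At wound-age HR 1, 2 and 3 the unstratified test rejected in 5.6%, 4.6% and 4.0% of trials, and the stratified test in 5.7%, 5.0% and 5.4% (simulation error about 0.35 points). The unstratified test is not inflated by wound age, and its conservatism is clear only at HR 3.

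**6. In subjects.** Required size scales with (1.96 + z_power)². At HR 2 with 50% older ulcers, z moves from 0.958 to 1.054, so 225 × [(3.014/2.918)² − 1] ≈ 15 subjects. At HR 3, z moves from 0.742 to 0.990, giving 225 × [(2.950/2.702)² − 1] ≈ 43.

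**The case against.** The strongest reply is that nothing here is an error. The unadjusted log-rank is a valid test, and the sample size was computed for exactly that test. Wound age is already a Cox covariate. Nothing in the documents shows that it affects healing enough to matter. Up to a wound-age HR of 2 the gain is at most about 2 points, and the standard formulas for this design already differ by 1.7 points among themselves (85.0% to 86.7%).

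Most of that stands, and it rules out several stronger readings that a reader might infer:
- **That the trial is shown to lose power.** The loss depends on a wound-age effect that the documents do not state. At HR 1 it is nil.
- **That the 86.1% is wrong, or the test invalid.** The figure reproduces, and the null rejection rates show no inflation from wound age.
- **That the analysis ignores wound age.** Only the log-rank omits it; the Cox model includes it in days.
- **That stratifying aligns the 12-week analysis with the randomisation.** That comparison sets Group 1A against Group 2B, after controls with less than 40% area reduction at TV7 have moved to Group 2C. It is selected on response, so balance within strata is no longer protected by randomisation. The simulations follow section 9.3 in treating these losses as non-informative drop-out, so the 12-week figures are not the power of that selected comparison.

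The reply does not remove the asymmetry. Stratifying by two levels costs at most 0.4 points in these runs if wound age is irrelevant, and gains power if it is not. A Cox model that waits for a significant log-rank result cannot supply that gain.

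**Conclusion.** The point holds as a free improvement with a minor efficiency gain. The primary log-rank test leaves out the only factor used to stratify randomisation. If wound age predicts healing, stratifying the 12-week test adds under 1 point of power at a between-stratum HR of 1.5, about 2 points at 2, and 4 to 7 points only near 3. It adds nothing if wound age is not prognostic. These figures rest on assumed wound-age HRs, assumed stratum shares, exponential healing and a common treatment HR within strata. The benefit is cleanest for the randomised 6-week comparison of Group 1A with Group 2A, where the gains are 0, 0.4, 1.3 and 4.5 points.

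**What to change.** In section 9.2 (H1) and section 9.7 (item 5), state that the primary time-to-heal comparisons use a two-sided log-rank test stratified by the wound-age stratum used at randomisation, with the unstratified log-rank as a sensitivity analysis. Include the same stratum in the Cox model, and exempt it from the section 9.7 rule that drops one of two variables correlated above 0.7, since it may correlate closely with wound age in days.

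Two clarifications belong with the change. H1 and item 5 should agree on whether the Cox model is run regardless of the log-rank result; running it unconditionally is simpler. Section 9.5 allows a new randomisation scheme with additional or modified strata, so the SAP should say which strata the primary test would then use.

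The cost is one SAP sentence in two places plus these clarifications. Wound age at S1 is already a required variable in section 9.7, so no data collection or sample size changes.

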5.2 INCLUSION CRITERIA

Potential subjects are required to meet all of the following criteria for enrollment into the study and subsequent randomization.

1. At least 18 years old.
2. Ankle Brachial Pressure Index (ABI) > 0.75. Calculations will be made using measurements from both posterior tibial and dorsalis pedis arteries as well as both arms AND/OR Skin Perfusion Pressures (SPP) greater than 30 mmHg OR Biphasic PVR OR TBI > 0.60 OR TCPO₂ > 30mmHg.
3. Presence of a VLU extending through the full thickness of the skin but not down to muscle, tendon, or bone. The largest ulcer will be designated the index ulcer and the only one included in the Study. If other ulcerations are present on the same leg the index ulcer must be 2 cm or greater in distance from the wound edge of the other ulcers.
4. Study ulcer (i.e. current episode of ulceration) had been present for at least one month (30 days) prior to the initial screening visit, and is excluded if it has undergone 12 month of continuous high strength compression therapy over its duration.
5. Study ulcer is a minimum of 2.0 cm² and a maximum of 25 cm² at the TV1 Randomization visit.
6. The target ulcer has been treated with documented full compression for at least 14 days prior to randomization.
7. Ulcer has a clean, granulating base with minimal adherent slough at the TV1 Randomization visit.
8. Females of childbearing potential must be willing to use acceptable methods of contraception (birth control pills, barriers, or abstinence). A urine pregnancy test must be administered during screening, and must be negative, for inclusion into the study.
9. Patient understands and is willing to participate in the clinical study and can comply with weekly visits and the follow-up regimen.
10. Patient has read and signed the IRB/IEC approved Informed Consent Form before screening procedures are undertaken.

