9.2 RESEARCH HYPOTHESES

Primary endpoints

H1: Time to heal

Time to heal after 12 weeks of CelluTome™ + SOC (**Group 1A**; maximum of 3 CelluTome™ applications) versus 12 weeks of SOC (**Group 2B**) will be equal for both groups or time to heal after 6 weeks of CelluTome™ + SOC (**Group 1A**; maximum of 2 CelluTome™ applications) versus 6 weeks of SOC (**Group 2A**) will be equal for both groups. Formally, $H_0: T_1 - T_2 = 0$; $H_A: T_1 - T_2 = D_1 \neq 0$, where T_1 is the time to heal for **Group 1A**, T_2 is the time to heal for **Group 2A or 2B** depending whether T_2 is 12 or 6 weeks, D_1 is the difference ($T_1 - T_2$) assuming the alternative hypothesis, and statistical test used is log rank applied to a Kaplan-Meier analysis. If either result is statistically significant, results will be adjusted using Cox regression and appropriate covariates.

Secondary endpoints

H2: Proportion of wounds healed

The proportion of wounds healed at 12 weeks after 12 weeks of CelluTome™ + SOC (**Group 1A**; maximum of 3 CelluTome™ applications) versus 12 weeks of SOC (**Group 2B**) will be equal for both groups. Formally, $H_0: P_1 - P_2 = 0$; $H_A: P_1 - P_2 = D_1 \neq 0$, where P_1 is the proportion of wounds healed for **Group 1A**, P_2 is the proportion of wounds healed for **Group 2B**, D_1 is the difference ($P_1 - P_2$) assuming the alternative hypothesis, and statistical test used is chi square.

H3: Incidence of Adverse Events (AEs)

The incidence of adverse events (AEs) by 12 weeks after 12 weeks of CelluTome™ + SOC (**Group 1A**; maximum of 3 CelluTome™ applications) versus 12 weeks of SOC (**Group 2B**) will be equal for both groups. Formally, $H_0: I_1 - I_2 = 0$; $H_A: I_1 - I_2 = D_1 \neq 0$, where I_1 is the incidence of AEs for **Group 1A** on a per subject basis, I_2 is same metric for **Group 2B**, D_1 is the difference ($I_1 - I_2$) assuming the alternative hypothesis, and statistical test used is the Mann-Whitney test.

H4: Correlation of wound area with protease activity at 4 weeks

The Pearson correlation coefficient (or Spearman's rho in the case of severe non-normality) calculated

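### The deciding test of time to heal leaves out starting ulcer area; if larger ulcers heal more slowly, a prespecified area-adjusted Cox test would gain power from data already collected

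*Combined protocol and SAP*

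**What the plan says.** - **Test for H1.** Section 9.2: "statistical test used is log rank applied to a Kaplan-Meier analysis". Cox regression with covariates follows only if one of the two results (6 or 12 weeks) is significant.
- **Final analysis.** Section 9.7, item 5, says the primary endpoints "will be analyzed by Kaplan-Meier and log rank test (unadjusted); and then Cox regression to adjust for the following variables". Initial area at randomization is one entry in a long covariate list. This section does not repeat the significance condition of 9.2.
- **Entry.** Section 5.2, criterion 5: "Study ulcer is a minimum of 2.0 cm² and a maximum of 25 cm² at the TV1 Randomization visit".
- **Randomization.** Section 9.4 stratifies by wound age only (1–6 months, over 6 months).
- **Data.** The variable list in 9.7 requires wound area as a continuous variable from TV1 onward.
- **Power.** Section 9.3 says a two-sided log-rank test on 113 control and 112 treatment subjects "achieves 86.1% power at a 0.05 significance level to detect a hazard ratio of 1.74". Half of the control wounds are assumed to heal.

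**The concern.** TV1 area is the baseline value of the quantity whose disappearance is the primary event. The entry criteria let it vary 25/2 = 12.5-fold, or log2(12.5) = 3.64 doublings. If larger ulcers heal more slowly, area explains part of the variation in healing time, and a test that uses it has more power on the same subjects.

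The planned Cox model contains area but cannot supply that power. Under 9.2 it runs only once the log-rank has succeeded. Under 9.7 it comes second and is not named as the test of H1. A chance imbalance in area between arms is likewise left unadjusted in the deciding test. What is at stake is some power at 12 weeks, and at 6 weeks, where there are fewer events and the plan states no power.

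**Working it through.** **1. Reproduce the stated power.** Inputs from 9.3: 113 and 112 subjects, control healing 0.5 at 12 weeks, hazard ratio (HR) 1.74, weekly loss 0.033 (control) and 0.0083 (treatment), no switching. Assume exponential healing and loss.

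- Healing hazards: control ln 2/12 = 0.0578 per week; treatment 1.74 × 0.0578 = 0.1005.
- Loss hazards: −ln(0.967) = 0.0336; −ln(0.9917) = 0.0083.
- Expected events = n × h/(h+d) × [1 − exp(−12(h+d))]: 47.6 + 75.4 = 123.0.
- Schoenfeld: √123.0/2 × ln 1.74 − 1.96 = 1.11, so power is 86.7%. Freedman gives 85.0%. Lakatos gives 85.7% with fine intervals and 86.0% with weekly intervals.

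The stated 86.1% is confirmed for the unadjusted log-rank. The same formula with 6 in place of 12 weeks gives 30.1 + 49.6 = 79.7 events and √79.7/2 × ln 1.74 − 1.96 = 0.51, about 70% power.

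**2. Add area.** The documents give neither the distribution of area nor its effect, so both are assumed. Area is log-uniform on 2–25 cm², and the healing hazard is proportional to area^(−b), which is 2^(−b) per doubling. The baseline hazard is set for 50% control healing at 12 weeks. The treatment effect is set so that treated healing is 1 − 0.5^1.74 = 70%, the marginal effect that 9.3 describes. Losses are as in step 1.

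The correlation of ln(area) with log healing time follows from rho² = 0.532b²/(1.645 + 0.532b²), where 0.532 = (ln 12.5)²/12 and 1.645 = π²/6.

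The table shows simulated power (%) for the log-rank, then for Cox with treatment and log area. Ranges are across repeated simulations. One 12-week set used hazard ratios per doubling of 0.7 and 0.6, shown in the b = 0.5 and 0.75 rows.

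| b | HR per doubling | rho | Conditional HR | 12 weeks | Gain | 6 weeks | Gain |
|---|---|---|---|---|---|---|---|
| 0 | 1.00 | 0 | 1.74 | 84–86 → 84–85 | about 0 | 67–69 → 67–69 | about 0 |
| 0.5 | 0.71 | 0.27 | 1.81 | 86–87 → 89–90 | about 3 | 71–73 → 73–75 | about 2 |
| 0.75 | 0.59 | 0.39 | 1.88–1.89 | 88–89 → 93–94 | 5–6 | 77–78 → 81–83 | 4–5 |
| 1.0 | 0.50 | 0.49 | 2.01 | 89–90 → 96–97 | 6–8 | 82–83 → 90–91 | 7–8 |

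For a weak association, the 12-week powers are 85.9% and 85.8% at an HR of 0.9 per doubling, and 86.7% and 87.3% at 0.8. Monte Carlo error is about 0.6 points, so these pairs are indistinguishable. Type I error with no treatment effect was 5.3% (log-rank) and 5.2% (Cox).

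**3. Where the gain comes from.** At b = 1 and 12 weeks, the standard error of the log hazard ratio was 0.185 unadjusted and 0.187 adjusted, so it does not shrink. The estimate grows. The unadjusted fit averages about 1.81, giving ln(1.81)/0.185 − 1.96 = 1.25, or 89%. The conditional HR is 2.01, giving ln(2.01)/0.187 − 1.96 = 1.77, or 96%. Both agree with the simulated powers.

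**The case against.** **The plan contains no error here.** A log-rank test is valid under randomization, and 9.3 powers exactly that test. With healing fixed at 50% versus 70%, the log-rank keeps about its planned 12-week power or more in every row of the table. This stands: the point concerns additional efficiency, not a shortfall.

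**The size is assumed.** This also stands. The top row of gains needs a steep gradient: at b = 1, 12-week control healing would be about 90% at 2 cm² and 17% at 25 cm². Nothing in the documents supports or excludes that.

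**Area is handled elsewhere.** Section 9.5 reviews area among the first 40 subjects and allows re-stratification if severe imbalances develop. Section 9.7 looks for baseline imbalances and lists area in the later Cox model. These steps limit or describe imbalance, but none restores power in the test that decides H1.

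**The simulation is not the planned 12-week comparison.** That comparison is Group 1A against Group 2B, after Group 2A subjects with less than 40% area reduction at TV7 have moved to Group 2C. Section 9.3 represents control losses by one rate, "The proportion dropping out of the control group is 0.033 per week", which is 1 − 0.967^12 = 33% over 12 weeks, and the simulation treats them as non-informative. The rate looks like (10% + 30%)/12 from section 5.1. No switching precedes TV7, so it overstates loss at 6 weeks; with 0.0083 in both arms, 6-week log-rank power at b = 0 is about 70% rather than 67%. These limits stand. Removing Group 2C is a separate problem that area adjustment does not solve.

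**Two stronger readings to avoid.**

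- A reader might apply the linear-model rule that adjustment multiplies the variance by 1 − rho². With rho = 0.5, (1.96 + 1.085)/√0.75 − 1.96 = 1.556, or 94%. That rule does not carry over to a Cox model, where the standard error did not fall, and the documents give no correlation.
- A reader might infer that the trial is underpowered. If 1.74 were the HR at equal area, log-rank power would be 81.1%, 76.6% and 70.5% at HRs of 0.7, 0.6 and 0.5 per doubling, against about 85% adjusted. But 9.3 attaches 1.74 to an unadjusted test and an overall control healing proportion, so it reads as the marginal effect.

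**Conclusion.** The point holds conditionally, as a low-cost improvement. The test that decides H1 ignores an available baseline measurement that the sponsor itself lists as an adjustment variable. If area is prognostic, adjusting for it raises 12-week power by about 3 to 8 points and 6-week power by about 2 to 8 over b = 0.5 to 1.0. If it is weakly prognostic or not prognostic, the change is about zero either way.

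These figures rest on log-uniform area, a log-linear area effect, exponential healing times, non-informative losses and no modelling of the Group 2C removal. The documents do not support saying that power is certainly lost, that the log-rank is invalid, or that 86.1% is wrong.

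**What to change.** In 9.2 (H1) and 9.7, item 5, make the confirmatory test at each time point the treatment term of a prespecified Cox model with three terms: treatment, ln(ulcer area at TV1) and the wound-age randomization stratum (1–6 versus over 6 months). Keep the unadjusted Kaplan-Meier curves and log-rank test as supporting displays. Remove the 9.2 condition that Cox follows only a significant result, so that 9.2 and 9.7 agree.

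Do not promote the existing covariate list. It contains infection episodes, which arise after randomization, site (up to 30 centers), and smoking status twice.

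The cost is SAP wording, with no new data, visits or subjects. The change must be made before outcome data are seen. The downside is that the reported hazard ratio becomes conditional on area and wound age and may lie noticeably further from 1 (about 1.8 to 2.0 against a marginal 1.74 for b = 0.5 to 1.0). The test then relies on proportional hazards and a log-linear area effect.

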5 STUDY POPULATION

5.1 NUMBER OF SUBJECTS

The study will consist of up to 30 centers in the United States each contributing about 10 subjects per center in order to obtain 300 evaluable subjects. We anticipate a 10% drop out rate during the trial for both Groups 1A and Group 2A, and 30% of subjects in Group 2A will switch to Group 2C and therefore a total of 225 subjects will be recruited. This trial employs an adaptive design therefore the enrollment numbers may be reduced or increased based on planned interim analysis.

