- Proportion of wounds healed at 12 weeks will be analyzed by chi square (unadjusted); this endpoint may also be analyzed using logistic regression to adjust for the following variables (with and without covariate imputation) if needed:
 - Site
 - Year enrolled (if trial lasts 2 years or more)
 - Treatment group
 - Initial area at randomization (cm²)
 - Initial wound depth (cm)
 - Age of wound at enrollment (days)
 - Smoking status
 - Prior VLU
 - Pain score at randomization

- Patient age
- Gender
- Ethnicity/race
- VCS score
- Diabetes
- Patient on pain medications
- Smoking status
- BMI
- Infection episodes

Note: unadjusted testing for **Group 2C** versus **2B** will be non-inferiority, followed by superiority testing if the former fails and proportion of wounds healed in **Group 2C** is much higher than in **Group 2B**.

- A summary of the incidence of adverse events (count by patient):
 - AE (category)
 - SAE (category; brief description; resolution; should include death)
 - When event happened in relation to start of treatment (days)
 - Associated patient ID, site ID

Incidence of AEs will be analyzed by Mann-Whitney test on a per subject basis.

- Correlation of changes in wound area with changes in protease activity will be first analyzed by calculating the Pearson correlation coefficient for each group or Spearman's rho if data are grossly non-normal. For each subject the change in protease activity is calculated by subtraction of the value at 4 or 8 weeks from the value at baseline; reduction in wound area is calculated similarly. Differences in r will be analyzed using Steiger's Z test with the assumption that r will have the same sign for both groups. If significant differences are found between groups, further analysis using GLM doubly multivariate repeated measures (change in wound area and protease activity between baseline and 4 and 8 weeks) to adjust for the following variables (with and without covariate imputation) may be undertaken (ordinal re-categorization will be done if data are severely non-normal):
 - Site
 - Year enrolled (if trial lasts 2 years or more)
 - Treatment group
 - Initial area at randomization (cm²)
 - Initial wound depth (cm)
 - Age of wound at enrollment (days)
 - Smoking status
 - Prior VLU
 - Pain score at randomization
 - Patient age
 - Gender
 - Ethnicity/race
 - VCS score

CELLUTOME™ IN VENOUS LEG

- Diabetes
 - Patient on pain medications
 - Smoking status
 - BMI
 - Infection episodes

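### The adjusted Cox model lists 17 variables, site among them, for about 80 to 108 healing events; with site as fixed terms its hazard ratio is inflated and its interval too narrow, though the log-rank test is untouched

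*Combined protocol and SAP*

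**What the plan says.** The primary test of time to heal is the unadjusted log-rank (sections 9.2 and 9.7). Section 9.7, Final Analysis, item 5 follows it with "Cox regression to adjust for the following variables (with and without covariate imputation". The list has 18 lines. Smoking status appears twice, so 17 variables are distinct, counting treatment, site, and year of enrollment (used only if the trial lasts two years or more).

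Section 5.1 plans "up to 30 centers in the United States each contributing about 10 subjects per center". Section 9.7 records site as an alphanumeric identifier and ethnicity/race as a multinomial factor. It does not say whether site is a fixed factor, a stratum or a random effect. It sets no limit on parameters, no penalisation and no pooling of small sites. The one reduction rule is to choose between two variables whose correlation exceeds 0.7.

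Section 9.2, H1 makes the model conditional: "If either result is statistically significant, results will be adjusted using Cox regression and appropriate covariates". Section 9.7 carries no such condition. Item 6 repeats the list for the proportion healed, where it is optional: "this endpoint may also be analyzed using logistic regression to adjust for the following variables".

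**The concern.** A Cox model with very few events per parameter tends to push the treatment coefficient away from the null and to report a standard error that is too small. The log-rank test gives a p-value and no effect size, and the adjusted Cox hazard ratio is the only hazard-ratio estimate that sections 9.2 and 9.7 specify. If it is biased and its interval too narrow, the benefit of grafting is overstated and its uncertainty understated, even when the primary test is sound.

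The two sections also give different instructions. Under 9.2 a trial with no significant log-rank result would have no planned hazard ratio; under 9.7 it would have one.

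**Working it through.** **Inputs.** Section 9.1.1: "all statistical testing will be two-sided and performed using a significance (alpha) level of 0.05". Section 9.3: "overall sample size of 225 subjects (113 in the control group and 112 in the treatment group"; the design "achieves 86.1% power at a 0.05 significance level to detect a hazard ratio of 1.74"; control healing 0.5; 12 weeks of follow-up; weekly dropout 0.033 (control) and 0.0083 (treatment). Section 5.1: up to 30 centers, and 30% of Group 2A moving to 2C.

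**Step 1. Reproduce the stated power.** With exponential healing, the control hazard is ln 2 / 12 = 0.0578 per week and the treatment hazard 1.74 × 0.0578 = 0.1005. Dropout hazards are −ln(1 − 0.033) = 0.0336 and −ln(1 − 0.0083) = 0.0083. Expected events per arm are n·λ/(λ+δ)·[1 − exp(−(λ+δ)T)]. At T = 12 this gives 47.6 control + 75.4 treatment = 123. Schoenfeld power is Φ(√(123/4) × ln 1.74 − 1.96) = Φ(5.545 × 0.554 − 1.96) = Φ(1.11) = 86.7%, against 86.1% stated. Freedman's formula gives 85.0% and a Lakatos-type model 85.7%. The planning inputs are therefore read correctly.

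**Step 2. Events in the planned comparisons.**
- 6 weeks, 1A versus 2A: 30.2 + 49.6, about 80.
- 12 weeks, 1A versus 2B: 113 × 0.70 = 79 remain in 2B. Taking healing as independent of the switch (an assumption), events are 47.6 × 79/113 + 75.4 = 33.3 + 75.4 = 108.7; simulated trials averaged 108.

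**Step 3. Parameters.** Site 29, year 1, treatment 1, continuous variables 7 (area, depth, wound age, pain, patient age, VCS score, BMI), binary variables 4 (prior VLU, gender, diabetes, pain medication), infection episodes 1, smoking 2, race and ethnicity 6: total 51. Omitting year or coding smoking as one ordinal term gives 49-50. With 15 sites the total is 36, and with no site terms 22. Events per parameter at 51 are 80/51 = 1.6, 108/51 = 2.1 and, using all 225 subjects at 12 weeks, 123/51 = 2.4.

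**Step 4. Simulation at the stated planning values.** 2,000 trials per scenario; covariates have no true effect unless marked; two-sided Wald test at 1.96. Type I error comes from the same setting with a hazard ratio of 1, and its Monte Carlo standard error is about 0.7 points.

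| Model and comparison | Events at HR 1.74 | Adjusted HR (true 1.74) | Type I error |
|---|---|---|---|
| 51 parameters, 12 weeks, 1A vs 2B | 108 | 2.09 | 11.3% |
| 51 parameters, 12 weeks, all 225 | 123 | 2.00 | 10.3% |
| 51 parameters, 6 weeks | 80 | 2.03 | 10.3% |
| 51 parameters, 12 weeks, all 225, prognostic covariates | 124 | 2.02 | 11.2% |
| 51 parameters, 6 weeks, prognostic covariates | 86 | 2.06 | 10.4% |
| 51 parameters, 12 weeks, all 225, weekly ties (Breslow) | 122 | 1.91 | 8.1% |
| 36 parameters (15 sites), 12 weeks, all 225 | 123 | 1.89 | 8.5% |
| 22 parameters (no site), 12 weeks, all 225 | 123 | 1.83 | 6.4% |

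With non-prognostic covariates and continuous healing times, the unadjusted model gives 1.73-1.75; across these scenarios its type I error is 4.3-5.8%. Repeat simulations of the 30-site model gave hazard ratios of 1.97-2.05 and type I errors of 10-12%. A 9-parameter model gave 1.75-1.76, about 95% coverage, and 5.2-5.7% type I error.

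**Step 5. The interval.** In the 51-parameter model with 123 events, the mean model standard error is 0.230 but the estimates have a standard deviation of 0.281. The bias is ln(2.00/1.74) = 0.139 and the half-width 1.96 × 0.230 = 0.451. Approximate coverage is Φ((0.451 − 0.139)/0.281) − Φ((−0.451 − 0.139)/0.281) = Φ(1.11) − Φ(−2.10) = 0.866 − 0.018, about 85%. Counting directly in simulated trials gave 84-90% across the 6- and 12-week comparisons.

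**Step 6. The condition in 9.2.** In null trials with 51 parameters, the unadjusted test (a Cox Wald test standing in for the log-rank) and the adjusted test are both significant in 2.5-3.8%. The condition does not protect the estimate. Among trials with a true hazard ratio of 1.74 that pass it, the adjusted hazard ratio averages about 2.0 to 2.4, partly because passing selects large effects.

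**The case against.** A reader might infer that the trial's false-positive rate doubles. The documents do not support that. The primary decision rests on the unadjusted log-rank, which the covariate list does not touch, and no section makes the Cox Wald test a success criterion. The 8-12% belongs to that Wald test read alone.

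A reader might also take the adjusted hazard ratio as the headline result. The documents do not designate a headline estimate. What stands is that no other hazard-ratio estimate is planned.

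The parameter count is fairly challenged too. About 50 requires all 30 sites to open and site to enter as 29 indicators, and the plan states neither. The year term is conditional, smoking is coded as ordinal, section 9.7 speaks of an initial list, and section 9.2 speaks of appropriate covariates. All of this makes 50 the upper case. It does not remove the problem: a correlation rule addresses collinearity, not events per parameter, and even without site terms the estimate is about 1.8.

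Finally, it is only under 9.2 that a non-significant trial would lack a hazard ratio. Section 9.7 fits the model regardless, so the supported point is that the two sections conflict.

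**Conclusion.** The point holds for the adjusted hazard ratio and its interval, and for nothing beyond them. With site as a 30-level fixed factor, a true 1.74 is estimated at about 1.9-2.1, the nominal 95% interval covers about 84-90%, and the Wald test of the adjusted model has about 8-12% type I error. With 15 sites the figures are about 1.89 and 8.5%, and with no site terms about 1.8 and 6-7%. The direction was the same in every scenario.

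These sizes rest on the section 9.3 planning values, exponential healing and assumed covariate distributions; making the covariates prognostic changed little. The largest uncertainty is how many sites open and how site is coded. The logistic model was not simulated. The conflict between 9.2 and 9.7 is in the text and needs no assumption.

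**What to change.** - Pre-specify one adjusted Cox model of about 8-10 parameters: treatment, the wound-age stratification factor, baseline area and a few named baseline prognostic variables.
- Do not enter site as up to 29 fixed terms. Use a site random effect (frailty), or leave site to a sensitivity analysis.
- Delete the significance condition in H1 so that sections 9.2 and 9.7 agree.
- Always report the unadjusted and the adjusted hazard ratio, each with a 95% confidence interval.
- If the optional logistic model in item 6 is fitted, use the same short list.

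The cost is SAP wording only. The downside is that fewer covariates appear in the adjusted model. The limit of 8-10 is a judgement; the simulated 9-parameter model supports it, but the documents do not dictate it.
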